This study is a longitudinal follow-up of 670 primarily African-American women and their 18-year-old firstborn children enrolled since 1990 in a randomized controlled trial (RCT) of prenatal and infancy home visiting by nurses. Nurses in this program are charged with improving pregnancy outcomes, child health and development, and maternal economic self-sufficiency.¹ This follow-up examines whether earlier program effects on maternal and child functioning²⁻⁷ lead to less violent antisocial behavior, psychopathology, substance use and use-disorders, and risk for HIV; whether these effects are greater for those who carry genetic susceptibility to the environment and are at environmental risk; and whether program effects replicate those found with whites in an earlier trial.⁸⁻¹⁰ Results from earlier phases of follow-up from this trial found that the Memphis program affected women's prenatal health, fertility, partner relations, and use of welfare; children's injuries, cognition, language, achievement, conduct, depression/anxiety, and use of substances through child age 12.²⁻⁷ Program effects on maternal life-course were concentrated among mothers with higher psychological resources (better intellectual functioning, mental health, and sense of mastery), probably because higher-resource mothers could envision their success in the world of work, leading to better pregnancy planning and employment. Program effects on children were greater for those born to mothers with low psychological resources, because without help, low-resource mothers are especially challenged in the care of their children and their children function less well. Given the damaging effects of early stressors on developing neural circuitry, and given that many early neural developmental insults do not become fully evident until synaptic pruning is complete in late adolescence and early adulthood, there was reason to expect this early intervention would have enduring effects at youth age 18.

Hypotheses for Primary Grant

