Tested with a primarily white sample in the Elmira trial, the NFP program produced effects consistent with the program model, that on average tended to be greater for families at greater social disadvantage and where mothers were more psychologically vulnerable.¹⁻¹⁰ These effects were translated into cost savings.^{175;176} The Memphis trial was designed to test the effects of the program with a large sample of very low-income African-Americans living in a major urban area, when the program was administered through a local health department, and the program developers had limited involvement in its implementation. In this trial, 1,138 low-income pregnant women (98% unmarried, 67% <19 years old, 92% African-American) were randomly assigned to experimental or comparison services; 742 were followed after delivery. The Memphis sample has resided in extraordinarily stressful neighborhoods and has endured extreme poverty. At registration, the mean level of neighborhood disorganization (assessed by census tract data at the block group and using the Lauritsen scale¹⁷⁷) was 3.43 SD above the national mean, i.e., the average level of adversity in the sample neighborhoods was among the worst in the nation (in the top 1000th). 85% of the sample had incomes below the federal poverty guidelines. Design details are provided below and in the published articles. The differences in

neighborhood disorganization among participants in the 3 trials of the NFP is illustrated in Figure 2.

Given results in Elmira, we hypothesized that program effects on parenting and child outcomes would be greater for the group defined by mothers having fewer psychological resources (poorer mental health, intellectual functioning, and self-efficacy/mastery). We found support for this hypothesis²⁻⁶ and that program effects on maternal life-course, especially in planning subsequent pregnancies, were concentrated among women with initially higher levels of psychological resources.⁶ We interpreted this as a reflection of nurse-visited higher-resource women's ability to secure employment and manage care of their children simultaneously, providing high-resource mothers with motivation to plan future pregnancies; nurse-visited low-resource mothers had difficulty balancing these tasks and envisioning success in the world of work, so they had fewer reasons to plan future pregnancies, and instead focused their resources on care of their children. Details of earlier findings are provided below.

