Maternal and Infant Outcomes

Prenatal Health, Care-Giving, and Injuries. Nurse-visited mothers, compared to control-group counterparts, exhibited superior prenatal health behaviors, fewer obstetric complications and infections, and better care of their children; their children had fewer health-care encounters for injuries/ingestions (Table 1). Program effects on care-giving and injuries were greater for mothers with low psychological resources. Figure 3 shows regressions of number of days children were hospitalized for injuries or ingestions from birth to age 2 on maternal psychological resources, fitted separately by treatment assignment. This figure emphasizes that the program effects on injuries and other child outcomes were concentrated on children born to mothers at greatest risk for compromised care-giving because of their limited psychological resources. Program impact on days hospitalized for injuries/ ingestions was limited to children with mothers in the lower half of the maternal psychological resource distribution (standardized to a mean of 100 and a standard deviation of 10). Table 1 shows that program effects on most child outcomes were greater for those born to the most vulnerable mothers. Discerning program impact on child abuse and neglect must be inferred from several sources of data (e.g., treatment-control differences in children's injuries revealed in their medical records, observations of infants' responses to their parents in laboratory observation paradigms), given that Tennessee child protection and child welfare records are not available prior to 2001, because of inadequacies in their earlier record keeping system. Moreover, such records under-estimate abuse¹⁷⁸ and are subject to surveillance bias.¹⁷⁹

[figure not shown]

Figure 2. Box and whiskers plots of the distributions of neighborhood disadvantage scores at registration for participants in the Elmira, Memphis, and Denver trials of the NFP.

Maternal Life-Course. As shown in Table 1, the program also produced consistent effects on maternal life-course (e.g., increased stability of partner relationships; reduced fertility, use of food stamps, and welfare). Effects on fertility outcomes, like closely spaced subsequent births (<2 years), were more pronounced for higher-resource mothers. At child age 9, as a trend, nurse-visited mothers also reported using fewer different types of substances ($p=.075$).

[figure not shown]

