We compared background characteristics among mothers and study children by treatment status for those eligible, but not seen with those eligible and seen this phase (see Tables S1 and S2 in appendix). Those not seen tended to more likely be non-African American, have low household poverty and lower scores on a measure of maternal beliefs associated with child abuse. However, there was no evidence for attrition related bias by treatment status. We have previously noted that at randomization there were differences between control and nurse-visited in household poverty and maternal beliefs associated with child abuse. We therefore have retained these as covariates as described in the statistical models section below.

In the process of tracing the sample for the 18-year follow-up, we uncovered a pattern of maternal and child mortality in which mothers and children in the control group appeared to have died more frequently than those visited by nurses, so we reviewed National Death Index records to ascertain patterns of maternal and child mortality over the first two decades following birth of the first child. The intervention-control difference in child mortality had been evident, as a trend, by child age 9, but given the infrequency of death for women and children in the age-ranges covered by this trial, we had not

hypothesized intervention effects on mortality. We present below the results of the mortality analysis through the current phase of follow-up.

Table 2. Sample Recruitment, randomization, attrition, and completed assessments at previous phases of the trial

Eligible Subjects Invited to Participate	1290				
Number Refused	151				
Number Randomized	1138				
Treatment Group Assignment	1	2	3	4	Total (TX 2 & 4)
Number Allocated to Each Treatment	166	514	230	228	742
Miscarriages (first born)	6	19	6	8	27
Stillbirths (first born)	0	5	3	2	7
Child deaths before age 18		11		2	8
Maternal Deaths before age 18		15		3	18
Mother declined before age 18		14		11	26
Lost to follow up (no current address) - mother		8		6	14
Passive refusal (have current address) - mother		20		5	25
Completed Mother 18 year assessment		426		192	618
Completed Other Custody assessment (for child behavior)		11		5	16
Lost to follow up (no current address) - child		20		9	29
Passive refusal (have current address) - child		9		2	11
Completed First Child 18 year assessment		435		194	629

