The primary analyses made use of general linear model methods and their extensions. The focus was on full model specification to account for all sources of variation, and a full examination of interactions among model factors. The primary classification factors for examination in our models, as determined by our hypotheses and earlier work, include treatments (Control vs. Nurse Visited - T), maternal psychological resources (low versus high – P), and sex of child (S). Standard covariates included an index of household poverty, maternal beliefs associated with child abuse, and for child outcomes, age of the child at the 18-year interview. Genetic analyses included the gene as an additional classification factor and were interacted with treatment status only (see more information below). We employed pared-down versions of full model specification when we had infrequently occurring outcomes (e.g. convictions for interpersonal violence). In general the approach involved beginning with a fully specified model and continuing to eliminate non-significant interactions unless a specific a priori hypothesis forced the interaction term(s) into the model.

Continuous variables were run with a general linear model; dichotomous variables with binomial error distributions; low frequency count variables with negative binomial distributions. For outcomes measured over the life course, the above models were extended to mixed or generalized mixed models to account for correlated data (random effects for time with unstructured variance terms). Subsequent children analyses were also run with mixed or generalized mixed models to account for correlation within the same family. We were interested in the treatment effects for subsequent children alone, as opposed to an overall family effect that would include the first born children.

We employed Cox proportional hazard models²³² for outcomes with a survival component. We present in the tables adjusted hazard rates at age 18 since the vast majority of the sample was interviewed after their 18th birthday but rapidly drops off after this date. The methods used for the mortality analyses can be found elsewhere.¹¹

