We examined mediation in models with simultaneous equations, testing the significance of direct and indirect effects and their equality using methods outlined by Mackinnon.²³³ We investigated models where the intervention had a significant effect through child age 2 on outcomes significantly different at this phase in the low psychological resource group.

While missing data in this trial were remarkably low, especially at this 18-year follow-up, we were sensitive to the potential pitfalls of only analyzing cases with complete data. We have a paper in the pipeline that indicates that at child age 12 estimates of treatment-control differences would have been reduced dramatically had we discontinued sample recruitment at levels retention often is considered acceptable for studies like this (70-80%), and that these reductions in treatment effects are not simply a reflection of statistical power or differences in measured baseline characteristics.¹⁸³ There are likely differences in life-course trajectories not explained by measured baseline characteristics. We have complete data on all relevant background characteristics. Our primary strategy has been to minimize attrition to greatest extent possible. We will consider comparing our analyses to the same analyses employing multiple imputation.²³⁴ For the multiple imputations, we generally would use a Markov Chain Monte Carlo method to impute enough data to have a monotone missing data pattern. Once we have a monotone missing data pattern, we would employ imputation approaches appropriate for the type of data (continuous, dichotomous, or low frequency count data). We will perform sensitivity analyses to ensure that results are similar under various assumptions. In general, given very low attrition, such approaches are not warranted.

Examination of Hardy-Weinberg Equilibrium. We calculated allele frequencies for each polymorphism examined in this study (5-HTTLPR, MAOA-LPR, COMT Val158Met) to determine whether

the sample is in HWE. Given the relatively small sample sizes involved in these calculations, we relied upon absolute deviations from HWE in addition to formal statistical significance in making determinations as to whether the polymorphisms are in HWE.²³⁶

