Inclusion of Gene Activity Classification Factors. Some of our models included classification factors for functional classifications (activity variants) of the polymorphisms hypothesized to moderate program impact in this trial (5-HTTLPR, MAOA-LPR, and COMT Val158Met); we were not interested in genotypes per se, but rather functional classes that group genotypes by activity level (low – L, high - H or intermediate - I). In the case of 5-HTTLPR, L_G and S alleles are both low-activity variants that lead to low expression; from the analysis standpoint, the low-activity genotypes (L_G/L_G, S/S, and L_G/S) were grouped into the low-activity class; the high activity genotypes (L_A/L_A) into a high-activity class; and the remaining genotypes (L_A/L_G and L_A/S) grouped into an intermediate class. We used a similar approach with MAOA-LPR and COMT Val158Met. In the case of the X-linked MAOA-LPR, we grouped males into high and low expression allele groups and excluded females from analyses. In the COMT Val158Met analyses, we excluded non-African ancestry participants.

Tests of Hypotheses

Maternal Outcome Hypotheses

Hypothesis 1 (primary): The program will continue to improve maternal life-course reflected in total costs for welfare (SNAP, AFDC/TANF, and Medicaid), especially for mothers with high psychological resources. We tested Hypothesis 1 by examining the primary maternal life-course outcome (public expenditures for SNAP, AFDC/TANF and Medicaid) in our primary model, estimating public expenditures for these benefits over time, which included a factor for T and P, the interaction between these classification factors (T x P), and a set of covariates. For the public benefit expenditure outcome, we analyzed the data in mixed models that included, in addition to the core model terms, women as levels of a random factor, a fixed repeated measures classification factor for time (first-born child age) of assessment, and all interactions of time with the other fixed classification factors. We examined the treatment–control difference summing across levels of maternal psychological resources, and conducted planned contrasts for women in the high-resource group.

Hypothesis 2 (secondary). The program will reduce maternal SUDs and depression. We examined SUDs and depression by examining planned contrasts within the classification structure specified for Hypothesis 1, using generalized linear models, logistic for depression and SUD.

Child Outcome Hypotheses

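### Youth cognitive, language and achievement models use maternal baseline resources only as a low/high class, giving up a modest amount of precision that data already held could recover

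*Protocol*

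**What the plan says.** The Study Overview describes the resource index by its parts: "mothers with higher psychological resources (better intellectual functioning, mental health, and sense of mastery". Preliminary Studies repeats the three components: "mothers having fewer psychological resources (poorer mental health, intellectual functioning, and self-efficacy/mastery". Under Maternal and Infant Outcomes the index is a continuous score, "standardized to a mean of 100 and a standard deviation of 10", and Figure 3 is described as regressing injury days on it.

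In Statistical Models and Methods of Analysis the index becomes a class: "maternal psychological resources (low versus high – P), and sex of child (S". The covariates follow: "Standard covariates included an index of household poverty, maternal beliefs associated with child abuse, and for child outcomes, age of the child". Household poverty and abuse-related beliefs are there because the arms differed on them at randomization. Research Activities for Current Phase of Follow Up says so: "We therefore have retained these as covariates as described in the statistical models section below". The missing-data paragraph adds: "We have complete data on all relevant background characteristics".

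Under Tests of Hypotheses, H3 sends roughly normal outcomes such as cognition and achievement to the general linear model with the saturated treatment by resources by sex structure. H6 then focuses the treatment contrast on children of low-resource mothers.

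**The concern.** In a linear model, a baseline variable that predicts the outcome lowers residual variance and hence the standard error of the treatment contrast. Cutting a continuous score in two loses part of that benefit. The covariates that were kept were chosen for imbalance, not for their ability to predict youth test scores.

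The loss falls on primary hypotheses, H3a and H6. It is sharpest for the H6 contrast. Within the low-resource class P is constant, so it explains none of the variation among those children, and the contrast uses only part of the sample. The cohort was enrolled in 1990–1991 and cannot be enlarged, so information already collected is a cheap place to look for precision.

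**Working it through.** The Protocol states no power, standard deviation or explained variance for the age-18 analysis, so there is no figure of its own to reproduce on this point. The completion rates do reproduce: 618/742 = 83.3% and 629/742 = 84.8%, against the stated 83% and 85%.

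**Inputs.** Table 2: 435 control and 194 nurse-visited youth assessed. Table 1: whole-sample and low-resource means with effect sizes. The Abbreviations define effect size as the mean difference over the pooled SD. Assumptions: two-sided alpha 0.05, equal halves for the low/high cut, and a normally distributed score.

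**Step 1: correlation of the composite with child scores (control arm).** With equal halves, high-resource mean = 2 × whole − low. SD = (nurse − control whole-sample mean)/ES. Then d = (high − low)/SD. Halves of a normal score lie 1.596 SD apart, so r = d/1.596.

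| Outcome | High mean | SD | d | r |
|---|---|---|---|---|
| KABC, age 6 | 2×90.24 − 87.64 = 92.84 | 2.10/.18 = 11.7 | 5.20/11.7 = .446 | .28 |
| PPVT, age 6 | 2×82.13 − 79.08 = 85.18 | 2.19/.17 = 12.9 | 6.10/12.9 = .474 | .30 |
| Achievement, age 12 | 2×87.94 − 85.66 = 90.22 | 1.29/.12 = 10.75 | 4.56/10.75 = .424 | .27 |

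**Step 2: gain from the continuous composite.** A median split keeps 2/π = 63.7% of the variance that the continuous score explains. After the score is added, the residual variance ratio is (1 − r²)/(1 − .637r²).

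- KABC: .922/.950 = .970, a 3.0% reduction; SE 1.5% smaller.
- PPVT: .912/.944 = .966, a 3.4% reduction; SE 1.7% smaller.
- Achievement: .929/.955 = .973, a 2.7% reduction; SE 1.4% smaller.

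If 40% to 60% of mothers are classed low, the range is 1.9% to 5.6%. Nurse-arm means imply less: 0.1% to 2.4% at a median split.

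**Step 3: a separate intellectual-functioning score.** Its correlation with youth scores is not given, so a range is assumed. The low/high class alone leaves about .946 of outcome variance (PPVT row). With the continuous covariate the residual is taken as 1 − r², which ignores anything P adds beyond it. Whole-sample SE = √(1/435 + 1/194) = 0.0863 in SD units. For the low-resource contrast at equal halves, SE = √(2/435 + 2/194) = 0.1221. Power is approximately Φ(ES/(SE × √v) − 1.96), where v is the residual variance.

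| Model | v | Reduction from .946 | Power, ES 0.20, whole | Power, ES 0.25, low-resource |
|---|---|---|---|---|
| Class only | .946 | – | 66% | 56% |
| r = .3 | .91 | 4% | 68% | 57% |
| r = .4 | .84 | 11% | 71% | 61% |
| r = .5 | .75 | 21% | 76% | 66% |

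At r = .2 the gain is about nil. ES 0.25 is the age-6 KABC low-resource effect in Table 1; ES 0.20 is illustrative.

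**Step 4: does the same hold for maternal depression?** The planned outcome is crossing a cut point, fitted as "using generalized linear models, logistic for depression and SUD". A simulation of 2,000 trials per setting used 426 and 192 mothers, a control rate near 30%, an odds ratio of 0.63 and slopes of 0.4, 0.7 and 1.0 per SD (all rates and effects assumed). It compared the class alone with the class plus the score. The SE of the log odds ratio rose from 0.209 to 0.211–0.217. Power rose by about 0.6 to 2.3 points because the conditional estimate moved further from zero.

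**The case against.** The strongest reply is that nothing here is false or contradictory. P is binary because the hypotheses and planned contrasts concern low- and high-resource groups. The word included does not show the covariate list to be exhaustive, and outcome-specific adjusters are often left to an analysis plan, which is not at hand. This limits the point to a missed improvement. It does not remove it, because this section itself fixes the coding of P and names the standard covariates while stating an aim of accounting for all sources of variation. Keeping P as a factor also does not prevent adding the score.

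Second, the gain is small on the Protocol's own figures. That stands. It may be smaller still, because abuse-related beliefs are already in the model and track the resource class. Control Bavolek means are 100.5 overall and 102.5 for low-resource mothers, so with equal halves the high mean is 98.5, SD = 1.8/.23 = 7.8 and d = 4.0/7.8, about .5. H3 also allows repeated measures for some outcomes, such as standardized math scores, which the single-time calculation ignores.

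Third, the section reports the models in the past tense, so a change now could be post hoc. That stands and governs how the added analysis should be labelled.

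Three stronger readings are tempting and are not supported:

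- **Maternal depression and anxiety (H2) tested with inflated standard errors.** These are cut-point outcomes, and depression is fitted by logistic regression. A prognostic covariate there does not shrink the SE of the conditional log odds ratio.
- **A clear gain for executive function (H5).** Those models already adjust for the youth's own KBIT Matrices and PPVT scores, beyond which maternal ability may add little.
- **Most of the baseline information is discarded.** A median split keeps about 64% of what the composite explains, and the weights of its components are not given.

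**Conclusion.** The point holds for the linear youth cognitive, language and achievement contrasts, H3a and the H6 low-resource contrast. Adding the continuous composite would cut residual variance by about 3% and the SE by about 1.5%, given r of about .27 to .30. That correlation is inferred from age-6 and age-12 control-arm means with rounded effect sizes, a normal score and equal halves. The cut used at age 18 is not stated.

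A reader might infer from Step 3 that the trial forgoes the equivalent of 13% to 26% more families (.946/.84 = 1.13; .946/.75 = 1.26). That needs a correlation of .4 to .5 for the separate intellectual-functioning score, which the Protocol neither gives nor excludes. It is an assumption, not a finding.

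This is a low-cost improvement to precision. It does not show bias or invalidate the planned tests. For maternal depression the most that can be said is about 1 to 2 points of power under the assumed slopes.

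**What to change.** In Statistical Models and Methods of Analysis, add the continuous baseline maternal intellectual-functioning score, or failing that the continuous resource score, as a fixed covariate in the youth cognitive, language and achievement models. Keep the treatment by resources by sex structure and the planned contrasts unchanged. If treatment differences have already been examined, report the adjusted models as a labelled sensitivity analysis beside the planned ones.

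The cost is one degree of freedom per model, no new data, and possibly a post hoc label. No change to the maternal depression, anxiety or executive-function models is asked for on this ground.
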